## **16. ADVERSE EXPERIENCES**

All adverse experiences (events) will be recorded at each visit throughout the duration of the trial or at any other occasion when they are diagnosed. The corresponding information should also be documented on the appropriate Case Report Form. The characterization of all adverse events will be performed according to the WHO dictionary. The following provides definitions of both adverse and serious adverse events that will be used in the trial.

### **16.1 Adverse event (AE)**

An AE is any untoward medical occurrence in a subject or clinical investigation subject administered a pharmaceutical product and that does not necessarily have a causal relationship with this treatment. An AE can therefore be any unfavorable and unintended sign (including an abnormal laboratory finding), symptom, or disease temporally associated with the use of a medicinal (investigational) product, whether or not related to the IMP.

### **16.2. Serious Adverse Event (SAE)**

Any untoward medical occurrence that at any dose:

- Results in death,

- Is life-threatening,
- Requires in-patient hospitalization ( $\geq 24$  hours) or prolongation of existing hospitalization,
- Results in persistent or significant disability/incapacity, or
- Is a congenital anomaly/birth defect.

All fatalities and serious adverse experiences (SAE), including serious clinical laboratory abnormalities even those that the investigator considers not to be related to the leg condition or the administration of the IMP must be immediately reported by phone, by email, or by fax to Hemostemix or its designee.

All significant symptoms and signs, which were not present at the previous visits, must be recorded as potential adverse experiences to be evaluated by the clinical investigator. Any medical condition present at the previous visits that remains unchanged or improves should not be recorded as an adverse experience at subsequent visits. However, if there is deterioration of a medical condition that was present at the initial visit, then this should also be considered a new adverse experience and reported.

If an SAE occurs, it will be noted and reported starting from the time point of the subject signing the Informed Consent Form, even if causality cannot be attributed to the IMP. AEs will be reported from Visit 2 onwards (time of blood draw for manufacture of the IMP).

### **16.3. Relationship to the IMP**

The investigator, using the following guidelines, should determine relationship between each adverse experience and treatment with the IMP.

**Not related:** The experience is clearly related to other factors such as the subject's clinical state or other therapeutic intervention.

- **Unlikely:** The experience was most likely produced by other factors such as the subject's clinical state, other therapeutic interventions, or concomitant drugs administered to the subject, and does not follow a known response pattern to the autologous ACP administration.
- **Possible:** The experience follows a reasonable temporal sequence from the time of the IMP injection and/or follows a known response pattern to autologous ACP administration, but could have been produced by other factors such as the subject's clinical state, other therapeutic intervention, or concomitant drugs administered to the subject.
- **Probable:** The experience follows a reasonable temporal sequence from the time of IMP injection and follows a known response pattern to the autologous ACP administration and cannot be reasonably explained by other factors such as the subject's clinical state, other therapeutic interventions, or concomitant drugs administered to the subject.

- ***Highly probable:*** The experience either occurs immediately following the IMP injection or there is a positive reaction at the application site, follows a known response pattern to the autologous ACP therapy, and cannot be reasonably explained by other factors such as the subject's clinical state, other therapeutic interventions, or concomitant drugs administered to the subject.

#### **16.4 Severity of adverse experience**

Severity of an adverse experience is defined as a qualitative assessment of the degree of intensity of an adverse experience, as is determined by the investigator or reported to him/her by the subject. The assessment of severity is made irrespective of relationship to the administration of the IMP or seriousness of the experience and should be evaluated according to the following scale:

- 1= Mild
- 2= Moderate
- 3= Severe
- 4= Life threatening
- 5= Death

#### **16.5 Actions to be undertaken by the PI**

AEs/SAEs are captured using an EDC. The following lists the procedures and written documentation for reporting SAEs including deaths:

- 1) All deaths have to be reported immediately by telephone to the company and subsequently in writing via fax or email within 24 hours using the Serious Adverse Experience (SAE) Report form. The corresponding information should also be documented in the Adverse Experience (AE) column in the CRF.
- 2) SAEs, which the investigator considers are not related to the clinical condition under study, must be reported by telephone to the company immediately and subsequently in writing using the SAE Report form within 24 hours. This includes SAEs and/or serious abnormal laboratory findings occurring during the entire trial period. The corresponding information should also be documented on the Adverse Experience (AE) column in the CRF.
- 3) All adverse experiences will be followed until resolution and/or until the etiology is established as not related to the administration of the ACP products using the AE follow-up CRF for non-serious AEs or the SAE Report form. If a subject requires long-term follow up because of a suspected adverse reaction to the IMP, a complete medical summary

with pertinent laboratory report is to be submitted to the company at the end of the follow-up period.

The investigator must inform the Ethics Committee/REB/IRB of any life-threatening toxicity, and all deaths according to local regulatory requirements.

#### **16.6. Expected adverse events**

A full list of expected adverse events is presented in Appendix 1.

### **17. DATA SAFETY MONITORING BOARD (DSMB)**

An independent DSMB, comprised of two experienced clinicians with relevant expertise (vascular surgery, cardiology, anesthesiology, trauma, stem cell technology) and a biostatistician serving the DSMB will blindly review the accumulated study data.

DSMB members and the unblinded biostatistician cannot be investigators involved in the conduct of the clinical trial and should have no vested financial interest in the company or in the outcome of the study and are not allowed to possess any shares or stock options in the company. DSMB members shall be reimbursed for their time and any out-of-pocket expenses incurred as part of their duties.

The company may designate one additional member to the DSMB, who will also coordinate the activity of the board.

The DSMB will be provided all study accumulated data, and schedule of meetings and role of DSMB will be outlined in a DSMB Charter to be signed and approved by all DSMB members.

### **18. WITHDRAWAL OF SUBJECTS FROM TRIAL**

The following events are considered sufficient reasons for a subject to discontinue the trial:

- Whenever the subject decides that it is in his/her best interest.
- Whenever the investigator considers it advisable or in the subject's best interest.

It is agreed that, for reasonable cause given by either the investigator or the Sponsor, the company may terminate this trial, provided a written notice is submitted at a reasonable time in advance of the intended termination.

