sufficient space to inject the entire 1 ml into each location in the foot. Therefore, a smaller volume should be injected into the remaining spots in the foot and save the additional volume for the leg injections. This additional volume of cells/placebo should be injected into additional spots in the leg. Thus, in such cases, there may be 1-2 additional injections into the leg. A treatment diagram (example shown below) will be used to document the injections administered to each subject.

- The measurements in the diagram below are only suggestions and the investigator should keep in mind that the principle is to cover as much of the ischemic area as possible. Therefore, he/she may need to reduce or increase the distance between the injection sites depending on the length of the limb.

The administration of the IMP is expected to take no longer than 20-30 minutes, after which the subject will continue to be tightly monitored for a period of 2 hours. The total volume will be 30 ml and approximately 0.75 -1 ml of cell suspension will be implanted into each of 30 injection sites, using a grid. A 23-gauge needle will be used.

The unblinded investigator should ensure that there are no clinical concerns that may prevent the subject from being able to receive the injection on the intended injection date. If the subject is not fit on the planned injection day, he/she should not be injected with the IMP (ACPs/placebo). This subject should be discontinued and if his/her health condition improves he/she can be re-screened into the study. Reasons for being unfit on the injection day include, but are not limited to: acute ischemia, cellulitis or other severe infection in the intended injection leg, wet gangrene, significant deterioration of clinical status, suspected severe concurrent disease with fever  $> 38.4^{\circ}\text{C}$ , etc.

The rationale for the dose of cells and volume is based on several literature reports. Specifically, based on studies of human EPC transplantation into nude mice, Iwaguro et al., calculated that satisfactory reperfusion of the hind limb would require 0.5 to  $2 \times 10^4$  endothelial progenitor cells/gram of animal weight

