### **20.7.1. Primary End-Point and Principal Analysis**

The primary efficacy end-point for this study is the earlier time from treatment with IMP to either de-novo gangrene, or doubling of wound size, or major amputation, or death. The time to the primary end-point will be presented by Kaplan-Meier curves stratified by treatment group.

The time from day of treatment with the IMP to the earlier time of either de-novo gangrene, or doubling of wound size, or major amputation, or death will be right censored by the subject's last follow-up date in the study.

The primary analysis for the between study groups comparison will be conducted utilizing the baseline adjusted Cox's proportional hazards (PH) model (SAS® PROC PHREG). In addition to treatment group and study site, baseline prognostic factors as will be defined in a more detailed SAP written prior to revealing of the blind will be included as covariates in the model.

The adequacy of the proportional hazards (PH) assumption will be confirmed by including a time dependent covariate for the active treatment group (as dummy variable) by log (time) interaction in the primary analysis model and testing it using 5% significance level. In case the PH assumption will be rejected the log rank test (SAS® PROC LIFTEST) will be used for statistical inference. A detailed sensitivity analysis of the principal analysis of the primary endpoint will be provided in a more detailed SAP to be sent to the Division prior to revealing of the blind and conduct of the pre-defined futility analysis.

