1.2.1. Study plan

The study consists of four periods: Screening, Treatment, safety monitoring and Long-term follow-up periods. Subjects will be followed for one year post treatment.

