3.2.1. Disposition of subject

Subject disposition will be tabulated for each treatment arm and overall by summarizing the number and percentage of subjects who are randomized, treated with the study treatments ACP-01 or placebo, included in each analysis set, and by the reason for early discontinuation (AE/SAE, major violation of study protocol, withdrawal of consent, lost to follow-up, death, suspected pregnancy, or other).

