3.3.2. Primary efficacy endpoint

3.3.2.1. Definition

The primary efficacy endpoint for this study is the earlier time from treatment with IMP to either de-novo gangrene in the treated limb, or doubling of wound size in the treated limb, or major amputation in the treated limb, or death. For subjects who were lost to follow-up or completed Month 12 study visit without a study event, the time to event will be censored by the subject's last follow-up date in the study.

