3.3.2.3. Sensitivity analyses

In order to assess the consistency of the primary analysis of time to event, sensitivity analyses will be carried out including:

- An unstratified log-rank test and the hazard ratio along with the associated 95% CI resulting from an unstratified Cox model (only treatment arm in the model).
- An analysis based on PP analysis set

Three additional sensitivity analyses will be performed to assess the robustness of the primary analysis results to the possible violation of the noninformative censoring assumption. The first sensitivity analysis assumes that subjects who discontinued without meeting any of the event criteria during the study had an event instead of being censored. The second sensitivity analysis will be based on the delta-adjusted method examined by Zhao et al. (2014). The third sensitivity analysis is an extension of the placebo-based pattern mixture model proposed by Lu (2014, 2015). The placebo-based pattern mixture model assumes that subjects who discontinued from the ACP-01 arm would have an event after discontinuation similar to that of placebo. The extended placebo-based pattern mixture model uses a sensitivity parameter to characterize the gradual deviation from the noninformative censoring underlying the primary analysis toward the informative censoring underlying the placebo-based pattern mixture model. The extended placebo-based pattern mixture model sensitivity analysis for time-to-event data is described as follows:

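### After the single Day 0 injection, leaving the trial also ends outcome follow-up: no deaths or treated-limb amputations are collected to Month 12 for subjects who discontinue

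*Protocol*

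**What the plan says.** - **Treatment.** Protocol 7.2 and 7.2.1 describe one administration session at Visit 3, Day 0: "The total volume will be 30 ml and approximately 0.75 -1 ml of cell suspension will be implanted into each of 30 injection sites". No further dose is scheduled.
- **Follow-up.** SAP 1.2.1, like protocol section 7: "Subjects will be followed for one year post treatment".
- **Leaving the trial.** Protocol section 18 gives two grounds for discontinuing the trial: the subject's own decision, and "Whenever the investigator considers it advisable or in the subject's best interest". It sets no criteria for the second, and says nothing about outcome data after either.
- **Recorded reasons.** SAP 3.2.1 tabulates early discontinuation by "AE/SAE, major violation of study protocol, withdrawal of consent, lost to follow-up, death, suspected pregnancy, or other".
- **Censoring, protocol.** In 20.7.1, time to the primary endpoint "will be right censored by the subject's last follow-up date in the study".
- **Censoring, SAP.** 3.3.2.1 reads: "For subjects who were lost to follow-up or completed Month 12 study visit without a study event, the time to event will be censored". Subjects who withdrew or were withdrawn are not named.
- **Sensitivity analyses.** SAP 3.3.2.3 shows how those subjects are treated in the primary analysis, because its first informative-censoring analysis assumes that "subjects who discontinued without meeting any of the event criteria during the study had an event instead of being censored". Two further analyses impute event times after discontinuation.

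**The concern.** After the injection there is no treatment left to stop, so a dosed subject who leaves the trial leaves only observation. Two of the four primary components, death and major amputation, can be established by telephone or from records without the subject attending. The plan censors such subjects and has no provision for looking for those events.

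Two things are at stake. One is precision: the SAP's final analysis needs 51 events from 65 subjects, and no sample-size section allows for dropout. The other is validity: censoring at discontinuation is harmless only if exit is unrelated to the coming event. The SAP itself plans for that assumption to fail, but an observed outcome is stronger evidence than an assumed one.

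**Working it through.** **Inputs.** Medians 3 months (placebo) and 7 months (ACP-01), exponential, 2:1 allocation (protocol 20.4, SAP 1.3). 65 subjects, 51 events, HR 0.43, one-sided 2.5%, 81% power (SAP 1.3). Follow-up 12 months. The withdrawal rate is not given; 5-30% over 12 months is an assumed range.

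**1. Reproduce the plan's figure.** Schoenfeld: power = Φ(√(d × 2/3 × 1/3) × ln(1/HR) − 1.96). With d = 51: √11.33 = 3.367; 3.367 × 0.844 = 2.841; Φ(0.881) = 81.1%. The stated 81% reproduces.

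**2. Expected events with complete follow-up.** Hazards are ln2/3 = 0.2310 and ln2/7 = 0.0990 per month.
- Placebo: 21.67 × (1 − 2^(−12/3)) = 21.67 × 0.9375 = 20.3
- ACP-01: 43.33 × (1 − 2^(−12/7)) = 43.33 × 0.6952 = 30.1
- Total 50.4, power 80.7%. This is already slightly under 51, so there is no slack.

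**3. Withdrawal at a constant rate, unrelated to outcome, then censored.** With a proportion q withdrawing over 12 months, η = −ln(1 − q)/12, and the probability of an observed event is h/(h + η) × (1 − exp(−12(h + η))). For q = 10%, η = 0.00878: placebo 21.67 × 0.9092 = 19.7; ACP-01 43.33 × 0.6666 = 28.9; total 48.6.

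| Withdrawn by 12 months (assumed) | Events | Events lost | Power |
|---|---|---|---|
| 0% | 50.4 | 0 | 80.7% |
| 5% | 49.5 | 0.9 | 80.0% |
| 10% | 48.6 | 1.9 | 79.2% |
| 15% | 47.6 | 2.8 | 78.4% |
| 20% | 46.6 | 3.8 | 77.5% |
| 30% | 44.6 | 5.9 | 75.7% |

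(Losses are taken before rounding.)

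**4. Probability that one departing subject later has an event.** For an event-free subject leaving at month c, P = 1 − exp(−h(12 − c)): at months 3, 6 and 9, 88%, 75% and 50% on placebo and 59%, 45% and 26% on ACP-01. An average over both arms must weight by who is still event-free. At month 6 that is 21.67 × 0.25 = 5.4 placebo and 43.33 × 0.552 = 23.9 ACP-01, or 4.4:1 rather than 2:1. The weighted averages are 66%, 50% and 29%.

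**5. When bias would arise.** In an illustrative simulation (65 subjects, 2:1, unstratified Cox, 4,000 runs), some subjects due an event are assumed to leave 0-2 months before it.
- True HR 1, 20% of events lost in both arms: mean HR stays near 1.
- True HR 1, 20% lost on ACP-01 only: mean HR 0.83; significant results favouring ACP-01 rise from 3% to 10%.
- True HR 3/7, 20% lost on placebo only: power falls from 83% to 56%.

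These one-sided losses are assumptions that show the mechanism, not estimates for this trial.

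**The case against.** **The reason list does not authorise withdrawal.** A reader might infer from SAP 3.2.1 that dosed subjects are removed for adverse events, protocol violations or suspected pregnancy. The documents do not support this. The list gives categories for a disposition table covering all randomized subjects. Some exits before dosing are expected: protocol 7.2 withdraws subjects after two failed batches, and 7.2.1 discontinues those unfit on injection day. This objection stands. What remains is that the list and section 18 do not match.

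**Safety follow-up continues.** Protocol 16.5 follows adverse experiences to resolution, so some later limb outcomes would surface. This stands in part. That follow-up may also end once an event is judged unrelated to the product, so it does not secure ascertainment to Month 12.

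**The plan already addresses informative censoring.** This is true. A reader might infer that lost outcomes are replaced by modelling. In fact the primary analysis simply censors, the first sensitivity analysis counts every discontinued subject as an event, and imputation is confined to the other two. These analyses bound the uncertainty but do not recover an ascertainable death or amputation.

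**A bias towards ACP-01 is not shown.** A reader might infer one. Investigators and assessors are blinded (protocol section 7), no section says that exits cluster before events, and equal loss in both arms left the HR near 1. The objection stands as to direction, but the documents do not exclude differential exit either.

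**The loss is small.** This stands. A figure of 4-5 events can be reached by placing all of 10-15% of subjects' exits at month 6 and averaging the arms 2:1. That timing is arbitrary, and the averaging ignores differential survival (step 4).

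**Conclusion.** The gap is real and modest in size. Protocol section 18 lets a dosed subject leave the trial without saying that outcome follow-up continues. Event-free leavers are censored, and neither document collects vital status or treated-limb amputation for them to Month 12. SAP 3.3.2.1 also leaves withdrawn subjects out of its censoring sentence, so their treatment has to be inferred from the sensitivity section.

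At an assumed 10-15% constant-rate withdrawal, the expected loss is 1.9-2.8 of about 50 events, and at 10% power falls from 80.7% to 79.2%. These figures rest on the planning medians, on outcome-independent exit, and on a withdrawal rate that the documents do not give. Only the death and amputation share, also not given, can be recovered without visits. Any material bias would require exits that are informative and unequal between arms. That remains an open possibility, not a finding. The case for change is that the missing information is cheap to obtain and bears directly on the primary endpoint.

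**What to change.** 1. **Protocol section 18.** Leave the withdrawal criteria as they are. Add that a dosed subject who discontinues for any reason other than withdrawal of consent to follow-up remains in outcome follow-up, with vital status and treated-limb major amputation collected by telephone or records through Month 12. For subjects who have already left, do this retrospectively, within consent and with ethics approval.
2. **SAP 3.3.2.1.** Count events so found in the primary analysis, name withdrawn subjects in the censoring rule, and state the censoring date for each discontinuation reason.
3. **SAP 3.2.1.** Reconcile the reason list with section 18, and tabulate exits before and after dosing separately.
4. **SAP 3.3.2.3.** Keep the existing sensitivity analyses. Gangrene and wound doubling will still be unobserved once visits stop.

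The cost is wording in both documents and modest tracing work: at the assumed 10-15% of 65, about 7-10 subjects, fewer once those who withdraw consent to follow-up are excluded. The SAP reports 65 subjects already treated at the April 2020 data export, so much of this may be retrospective, and some subjects may not be traceable. Dosing, visits and clinical care do not change.

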### **19. ETHICAL AND REGULATORY ISSUES**

#### **19.1. Informed consent**

Informed consent for each subject will be obtained prior to initiating any trial procedures in accordance with the statement entitled "Requirements for Informed Consent." According to the existing laws and regulations, one copy of the informed consent form must be given to each subject and one signed copy must be retained in the investigator's trial records.

The “Declaration of Helsinki” recommends that consent be obtained from each potential subject in biomedical research trials after the aims, methods, anticipated benefits, and potential hazards of the trial, and discomfort it may entail, are explained to the individual by the physician. The subject should also be informed of his or her right not to participate or to withdraw from the trial at any time. If the subject is in a dependent relationship to the physician or given consent under duress, the informed consent should be obtained by an independent physician. If the subject is legally incompetent (i.e., a minor, or mentally incompetent), informed consent must be obtained from the parent, legal guardian, or legal representative in accordance with the law of the country in which the trial takes place. By signing this protocol, the investigator agrees to conduct the trial in accordance with the “Declaration of Helsinki.”

